4.9 Data Elements

Once referred for screening, the participant's diagnostic testing will be reviewed to assure that the correct OI classification has been made and eligibility requirements are met based on study inclusion and exclusion criteria. Data will be collected at study visits per the **Schedule of Events for each study group**. We will use a variety of methods to obtain these data. Certain information will be obtained from a historical review of existing charts and laboratory/treatment data. Other data will be obtained from patients or their families through a standard interview, examination or laboratory/functional testing. The investigators who will perform functional assessments and other critical evaluations will be included as investigators on their local institution's IRB application.

Medical History: Medical history will be recorded on a history and physical examination form.

12-lead EKG: EKG at the screening visit then at 2 subsequent study visits for all study participants.

Bone mineral density: A dual-energy x-ray absorptiometry (DXA) at the lumbar spine, total hip and femoral neck will be performed.

X-rays of the spine: Standard posterio-anterior and lateral views will be taken, preferably in the standing position. If this is not possible, these radiographs will be obtained in the sitting position. If participants not able to sit, the X-rays will be taken in the supine position. Taking each of the two views on a single film (skull base to sacrum) is preferred. All radiographic images will be reviewed at the screening visit to determine eligibility. Historical surveys are acceptable if X-rays taken demonstrate the boney abnormalities that are required as inclusion criteria.

Peripheral Quantitative CT of the forearm: A peripheral quantitative CT (pQCT) will be performed at Baseline and exit visits for those subjects participating in the 2nd stage of the study to determine bone mineral density. Measurements will be performed at the non-dominant forearm. In case of recent fracture (< 2 years before) or the presence of metal at this measurement site, the contralateral forearm will be used. Two sites at the forearm will be analyzed, the metaphysis ('4% site') and the diaphysis ('65% site'). Trabecular bone is analyzed at the 4% site, cortical bone is analyzed at the 65% site. The main outcome measures of these analyses are trabecular volumetric bone mineral density (vBMD, 4% site), cortical vBMD (65% site), bone mineral content (both sites) and section modulus (a measure of bone strength, 65% site).

Pulmonary function tests: These will be performed in participants enrolled in the 2nd stage of the study at baseline and exit visits, according to the American Thoracic Society guidelines. Lung volume measurements will be determined by helium dilution. Arm span will be measured to obtain a corrected height and will be used for calculating predicted lung volumes and flow rates. Vital capacity (VC), residual volume (RV), total

lung capacity (TLC), forced vital capacity (FVC), forced expiratory volume in 1 second (FEV1), and FEV1/FVC will be calculated for each participant to determine whether participants suffer from pulmonary compromise due to an underlying tissue disorder, which may go unrecognized without PFT, or if scoliosis is the actual cause for pulmonary compromise. Restrictive lung disease will be defined as a reduction in the VC and a ratio of FEV1/FVC greater than or equal to 80%. Obstructive lung disease will be defined as a reduction in FEV1 and a ratio of FEV1/FVC less than 80%⁸.

6 Minute Walk Test: A 6 minute walk test will be performed at the baseline and exit visits for those subjects enrolled in the 2nd stage of the study to determine the subject's mobility.

Numeric Rating Scale: Pain will be evaluated using the Numeric Rating Scale (NRS). This is a self-report assessment scale for patients who are able to use numbers to rate the intensity of their pain.

PROMIS® 29: This tool will be assessed at the screening, day 180 and day 360 study visits for participants enrolled in the 2nd stage of the study.

All study elements are interpreted locally by the respective PIs.

All laboratory testing will be performed using local laboratories and will be interpreted by the respective PIs.

NIH APPROVED

4.10 Schedule of Events

Procedures	Screening	Treatment				
		1	15	30	90	180
	-60 d window	±3 d window		±7 d window		
Informed Consent	X					
Medical History	X					
Physical Examination	X		X	X	X	X
Vital signs - heart rate, blood pressure, respiratory rate, and body temperature	X	X	X	X	X	X
Height	X					
Weight	X					
Blood/Urine for Safety labs (CBC, CMP, PT/INR, Urinalysis OR Urine Dipstick)	X		X	X	X	X
Blood for Bone remodeling markers (P1NP, Osteocalcin, CTX)	X			X	X	X
Blood for Vitamin D testing	X					
Blood for lymphoblast culture	X			X		
Urine Pregnancy test (if applicable)	X	X				X
Blood for Genetic Testing for COL1A1 , COL1A2 , CRTAP , P3H1 , or PP1B mutations ^a	X					
Skeletal survey ^b	X					
12 Lead EKG	X		X			X
DXA Lumbar Spine ^c		X				X
DXA total hip and femoral neck ^a		X				X
Infusion of fresolimumab		X				
Pharmacokinetics		X ^e	X	X	X	X
Adverse event documentation		X	X	X	X	X

a Genetic testing will be done only if the genotype is not known

b If skeletal films are available for review to ascertain the bony deformities or scoliosis, this test will not be done

c Test may not be performed if there is significant scoliosis or the patient has had spinal instrumentation

d Test may not be done if there are pins or rods in the region of interest

e For Day 1 of the study, PK samples will be obtained prior to the infusion of fresolimumab and after the end of the infusion.

Repeat Dose Administration (Stage 2)							
Procedures	Screening	Treatment					
		1	15	30	90	180	270
	- 60 d window	±3 d window		± 14 d window			
Informed Consent	X						
Medical History	X						
Physical Examination	X		X	X	X	X	X
Vital signs - heart rate, blood pressure, respiratory rate, and body temperature	X	X	X	X	X	X	X
Height	X						X
Weight	X						X
Arm-span	X						X
Blood/urine for Safety labs (CBC, CMP, PT/INR, Urinalysis OR Urine	X		X	X	X	X	X
Blood for Vitamin D testing	X						
Bone remodeling markers (P1NP, Ocn, CTX)	X			X	X	X	X
Blood for PK ^a		X	X	X	X	X	X
Blood for lymphoblast culture	X		X	X	X		X
Blood for Antibody/Immunogenicity testing		X	X	X	X	X	X
Blood for Genetic Testing for COL1A1, COL1A2, CRTAP, P3H1,	X						
Urine Pregnancy test (if applicable)	X	X			X	X	X
Skeletal survey ^b	X						
12-lead EKG	X		X		X		X
Infusion of fresolimumab		X			X ^f	X	X ^f
DXA Lumbar Spine ^c		X					X
DXA total hip and femoral neck ^a		X					X
Peripheral quantitative CT (pQCT) of the forearm ^e		X					X
NRS		X			X	X	X
PROMIS® 29 QOL		X			X		X
Pulmonary function test		X					X
6-minute Walk test		X					X
Adverse event documentation		X	X	X	X	X	X
Bleeding Assessment ^g			X	X			

a Genetic testing will be done only if the genotype is not known,

b If skeletal films are available for review to ascertain the bony deformities or scoliosis, this test will not be done
c this test may not be performed if there is significant scoliosis or the patient has had spinal instrumentation

d this test may not be done if there are pins or rods in the region of interest

e Will not be performed if bone deformities preclude assessment

f Will not be performed if subject is randomized into the study group to receive 2 infusions.

g Any patient who experiences clinically significant bleeding will be referred to their primary physicians or hematology specialists for appropriate work up

PK samples will be obtained prior to the infusion of fresolimumab and after the end of the infusion.

NOTE: For documentation of AE and safety, specific information regarding including history of bleeding episodes, physical examination for peripheral edema, hematomas, and gingival hyperplasia, and urinalysis OR a urine dipstick to evaluate for blood will be conducted.

5. Data and Safety Monitoring Plan

The study protocol will be reviewed and approved by the National Institutes of Health (NIH) before submission to individual center IRBs for approval. Participant enrollment may only begin with IRB approved consent forms.

5.1 Study Oversight

The Study Chair has primary oversight responsibility of this clinical trial. The NIH appointed Data Safety Monitoring Board (DSMB) has oversight responsibility of the Data Safety Monitoring Plan (DSMP) for this clinical trial. The DSMB will review accrual, patterns and frequencies of all adverse events, and protocol compliance every 6 months. The DSMB makes recommendations to the NIH regarding the continuation status of the protocol.

Each site's Principal Investigator and their research team (co-Investigators, research nurses, clinical trial coordinators, and data managers) are responsible for identifying adverse events. Aggregate report- detailed by severity, attribution (expected or unexpected), and relationship to the study drug/study procedures – will be available from the DMCC for site review. Adverse events will be reviewed monthly by the research team. A separate report detailing protocol compliance will also be available from the DMCC for site review on a monthly basis. The research team will then evaluate whether the protocol or informed consent document requires revision based on the reports.

5.2 Adverse Event Definitions and Standards

The Rare Diseases Clinical Research Network defines an adverse event as: "...an unfavorable and unintended sign, symptom or disease associated with a participant's participation in a Rare Diseases Clinical Research Network study."

Serious adverse events include those events that: "result in death; are life-threatening; require inpatient hospitalization or prolongation of existing hospitalization; create persistent or significant disability/incapacity, or a congenital anomaly/birth defects."

An unexpected adverse event is defined as any adverse experience, the specificity or severity of which is not consistent with the risks of information described in the protocol.

Expected adverse events are those that are identified in the research protocol as having been previously associated with or having the potential to arise as a consequence of participation in the study.

All reported adverse events will be classified using the current version of the Common Terminology Criteria for Adverse Events (CTCAE) developed and maintained by CTEP at National Cancer Institute.

5.3 Expected/ Known Risks/ Discomforts/ Adverse Event Associated with Study Intervention and Procedures: Definition of Expected Adverse Events

Study Drug

TGF β is a cytokine that has an important physiological role in the regulation of cell proliferation and differentiation, extracellular matrix production, angiogenesis, immune regulation and embryonic development. However, sustained overactivity of TGF β may play a pathophysiological role in disease states such as fibrotic diseases such as FSGS, IPF, and in oncology. Fresolimumab, a human IgG4 antibody which neutralizes TGF β 1, 2, and 3, has potential in the treatment of fibrotic and oncologic diseases. Given the pleiotropic effects of TGF β , side effects associated with fresolimumab therapy may be observed. The following is a description of potential risks, precautions, and contraindications based on the results of preclinical safety studies and clinical data.

Epithelial Changes Including Keratoacanthoma

Across the clinical studies, the majority of bleeding adverse events reported have been mild, self-limited events of gum bleeding without associated gingival lesions and nose bleeding without discrete nasal lesions. Anemia was not seen with these mild, self-limited events. Patients should be carefully monitored for the development of anemia and bleeding while receiving fresolimumab.

Immune Modulation

In preclinical studies, there did not appear to be any significant immune-mediated toxicity associated with long-term neutralization of TGF β in normal mice. No evidence of significant immune dysregulation has been seen in clinical studies to date. Three patients with malignant melanoma and 1 patient with FSGS developed non-disseminated herpes zoster. The FSGS patient had a history of herpes zoster. In 1 of the 4 patients, the herpes zoster event was considered by the reporting physician to be related to therapy. It remains to be determined if fresolimumab increases the risk of herpes zoster. Patients should be carefully monitored for the development of herpes zoster. One FSGS patient developed transient vitiligo and 2 oncology patients developed hypopigmentation of skin or hair. In all 3 patients, the events were considered by the reporting physician to be treatment-related. The mechanism by which fresolimumab could be associated with vitiligo/hypopigmentation could potentially be via immune modulation however alternative non-immune mechanisms may play a role.

Reproductive Function

The effects of fresolimumab on male and female reproductive function or fetal growth and development have not been investigated in formal toxicity studies. Maternal TGF β levels are elevated during normal pregnancy and may have an important role in establishment and preservation of pregnancy. Additionally, TGF β has a role in embryonic development including organogenesis. Fresolimumab is an antibody and is expected to be able to cross the placenta and enter the fetal circulation during pregnancy. The effects of fresolimumab in this situation are unknown. There is a theoretical risk that inhibiting TGF β during pregnancy may adversely affect the establishment and preservation of pregnancy or have adverse effects on embryonic or fetal growth and development. Pregnant or lactating women are excluded from clinical studies of fresolimumab. Women who become pregnant or start lactating during the study will be discontinued from study treatment. Sexually active men or sexually active women of childbearing potential (premenopausal and not surgically sterile) must use contraception or abstinence when being treated with fresolimumab.

Overdose

Animal studies have not clearly identified any acute dose related toxic effects. In the event of fresolimumab overdose, the administration should be immediately discontinued and appropriate precautions should be taken.

Contraindications and Warnings

There are no established contraindications to fresolimumab. Patients with significant hypersensitivity to fresolimumab or product components are excluded from clinical studies with fresolimumab. Continued treatment with fresolimumab should be carefully re-evaluated if significant hypersensitivity is observed. Pregnant or lactating women are excluded from clinical studies of fresolimumab. Women who become pregnant or start lactating during the study will be discontinued from study treatment.

Study Procedures

Blood samples will be drawn for safety labs. It is expected that there may be bruising and mild discomfort at the site of needle insertion when phlebotomy is performed. Fainting may even occur.

Participants will be exposed to radiation during dual-energy X-ray absorptiometry scanning and radiographs. The total amount of radiation that the participant will receive in this study is about 1.1 mSv or 110 mrem, and is approximately equivalent to a uniform whole body exposure of 133 days of exposure to natural background radiation. (Ref <http://www.doseinfo-radar.com/RADARDoseRiskCalc.html>). Though the biological effects of diagnostic radiation on humans have not been studied directly, the potential risk to an individual associated with techniques used for the assessment of bone status is believed to be very small since radiation doses are low. In 2012 the United Nations Scientific Committee on the Effects of Atomic Radiation stated that for typical background radiation levels (1–13 mSv per year), it is not possible to account for any health effects.

Patients may find the pulmonary function testing, function and mobility assessments and hearing tests to be tiring.

Protection from Risk: The study will be conducted in the Clinical and Translational Science Award (CTSA) Centers or research facilities of our respective institutions comprising the BBD Consortium whenever possible. When a CTSA/research facility is not available, study visits will be conducted in the investigator's clinic.

The study implementers will be nursing staff/coordinators of the Centers with a long experience in care of individuals with OI. If any participant should incur any unexpected and untoward event during the testing procedure, the emergency caregivers, would become available on an immediate basis to provide necessary emergent management.

Female participants will have no radiographic procedures while pregnant.

5.4 Adverse Event Reporting Timeline

- Within **24 hours** (of learning of the event), investigators must report any reportable Serious Adverse Event (SAE) that:
 - Is considered life-threatening/disabling or results in death of subject
 - OR-
 - Is Unexpected/Unanticipated
- Investigators must report all other reportable SAEs within **5 working days** (of learning of the event).
- All other (suspected) reportable AEs must be reported to the RDCRN within **20**

working days of the notification of the event or of the site becoming aware of the event.

Local institutional reporting requirements to IRBs, any GCRC oversight committee and the FDA, if appropriate, remain the responsibility of the treating physician and the Study Chair.

5.5 RDCRN Adverse Event Monitoring System (AEMS)

The study will utilize the DMCC Adverse Event Monitoring System. Upon entry of a serious adverse event, the DMCC created AEMS will immediately notify the Study Chair, site PIs, the Medical Review Officer, and any additional agencies (if applicable-industry sponsor, CTEP) of any reported adverse events via email.

Serious adverse events: The NIAMS OSMB/DSMB Safety Officer reviews the causality assessment determined by the PI and comment on attribution and recommend any needed action. A back-up notification system is in place so that any delays in review by the NIAMS OSMB/DSMB Safety Officer beyond a specified period of time are forwarded to a secondary reviewer. The DMCC Adverse Event Monitoring System maintains audit trails and stores data (and data updated) and communication related to any adverse event in the study.

Non-serious expected adverse events: Except those listed above as immediately reportable, non-serious expected adverse events that are reported to or observed by the investigator or a member of his/her research team will be submitted to the DMCC in a timely fashion (within 20 working days). The events will be presented in tabular form and given to the NIAMS OSMB/DSMB Safety Officer on a biannual basis. Local site investigators are also required to fulfill all reporting requirements of their local institutions.

The DMCC will post aggregate reports of all reported adverse events for site investigators and IRBs.

5.6 Unanticipated Problem Reporting

The Office for Human Research Protections (OHRP) considers unanticipated problems involving risks to subjects or others to include, in general, any incident, experience, or outcome that meets **all** of the following criteria:

- unexpected in terms of nature, severity, or frequency given (a) the research procedures that are described in the protocol-related documents, such as the IRB-approved research protocol and informed consent document; and (b) the characteristics of the subject population being studied;
- related or possibly related to participation in the research (“possibly related” means there is a reasonable possibility that the incident, experience, or outcome may have been caused by the procedures involved in the research); and
- suggests that the research places subjects or others at a greater risk of harm (including physical, psychological, economic, or social harm) than was previously known or recognized.

Per the definition, only a subset of adverse events would be characterized as unanticipated problems. There are other types of incidents, experiences, and outcomes

that are not considered adverse events, but are characterized as unanticipated problems (e.g., breach of confidentiality or other incidents involving social or economic harm). Incidents or events that meet the OHRP criteria for unanticipated problems are to be reported to the IRB, per local institutional reporting requirements. Local institutional reporting requirements to IRBs, any GCRC oversight committee and the FDA, if appropriate, remain the responsibility of the treating physician and the Study Chair.

5.7 Study Discontinuation

The NIH, RDCRN DSMB and local IRBs (at their local site) have the authority to stop or suspend this trial at any time. This study may be suspended or closed if:

- Accrual has been met.
- The study objectives have been met.
- The Study Chair / Study Investigators believe it is not safe for the study to continue.
- The RDCRN DSMB suspends or closes the trial.
- The NIH suspends or closes the trial.
- The FDA suspends or closes the trial.
- If 2 or more subjects experience Grade 4 or higher adverse events as defined by the CTCAE or life threatening AEs not covered by the CTCAE of the same preferred term related to the study medication, excluding conditions present at baseline or those directly related to skeletal complications of Osteogenesis Imperfecta.
- If 2 or more subjects develop cancer.

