Statistical Considerations (sample size and analysis plan):	
This study is designed to assess the safety and tolerability of fresolimumab in patients with Osteogenesis Imperfecta.
 
Sample Size: No formal sample size calculations will be done for this study. The sample size was selected to allow for an initial assessment of safety in this population, dose range and feasibility of enrollment in this rare disorder. The sample size is 8 for the single dose study and 8 for the repeat dose study. Participants enrolled in Stage 1 of this study may be enrolled in Stage 2 of the study if they meet eligibility. The overall enrollment will be 16. If needed, 2 additional patients will be enrolled in the repeat dose study to account for a dropout rate of 20%.
 
Treatment-Related Adverse Events will be summarized by dose groups. Changes in Vital signs (heart rate, blood pressure, respiratory rate, and body temperature), EKG, changes in laboratory assessments and physical examination findings, and patient-reported symptoms will be described. These variables will assess the primary endpoint of safety. Percent change in bone remodeling markers will be analyzed using a mixed model. BMD in the lumbar spine and the hip at 6 months for the single dose study and at 12 months for the multiple dose study will be compared to pretreatment levels using a Wilcoxon Signed Rank test. Percent change in the variables of the pulmonary function tests, and changes in the 6-minute walk test and the Numeric Rating Scale (NRS) for pain will be evaluated by Wilcoxon Signed Rank test. Values for derived pharmacokinetic variables, including Cmax, area under the curve, distribution, half-life (T1/2a), elimination half-life (T1/2b), clearance (CL), and volume of distribution at steady state (Vss), will be calculated as previously described and summarized by dose-group using descriptive statistics.

Sponsors (federal, state, foundation and industry support):	National Institutes of Health (NIH), The Osteogenesis Imperfecta Foundation (OIF), Genzyme

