3.5 Fresolimumab for inhibition of TGF β in humans

The safety of fresolimumab has been evaluated by Genzyme in non-clinical studies using rodent and non-human primate models. Fresolimumab has also been used in humans with idiopathic pulmonary fibrosis, idiopathic focal segmental glomerulosclerosis¹⁸, advanced renal cell carcinoma and malignant melanoma¹⁹ in Genzyme-sponsored clinical studies. The nonclinical and clinical data gathered to date support single- and repeat-dose administration of fresolimumab in humans.

The effects of fresolimumab on bone turnover and bone mass have not been studied, and the sponsor wishes to conduct a phase I study of fresolimumab in a Mendelian skeletal condition with proven over-activity of TGF β . This would be the first disease-specific therapy to be investigated in humans with OI.

[figure not shown]
4. Study Design and Methods

This is a multicenter, phase I study to evaluate the safety of single and repeat dose administration of fresolimumab in adult patients with moderate-to-severe OI. Stage 1 will involve a single dose of fresolimumab wherein those in group 1 will be administered a dose of 1 mg/kg body weight and those in group 2 will be administered a dose of 4 mg/kg body weight; there will be no randomization in this stage. Stage 2 will involve repeat doses of fresolimumab; in this stage, the Data Management Coordinating Center will randomize patients into two groups – individuals in group 1 will receive 4 doses of fresolimumab at months 0, 3, 6, and 9 and individuals in group 2 will receive two doses of fresolimumab at months 0 and 6.

Design

After the four individuals complete the 1 mg/kg dose (group 1, stage 1), an independent Data Safety and Monitoring Board appointed by the National Institute of Health will review the safety data. The decision to proceed with the 4 mg/kg single dose administration (group 2, stage 1) will be determined by the DSMB based on adverse events, safety data collected, and discontinuation criteria outlined in sections 5.6 and 5.7 of the protocol.

If the study proceeds, the study procedures for the 4 mg/kg (group 2, stage 1) will be identical to those for the 1 mg/kg (group 1, stage 1). After completion of the single dose infusion of 4 mg/kg (group 2, stage 1), the DSMB will assess the safety profile of the dose and provide a decision regarding the repeat dose studies (Stage 2).

Study Sites

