5.8 Subject Discontinuation

An intent to treat approach will be used. All data acquired prior to termination for the reasons outlined below will be included in the primary analysis unless patient withdraws consent. Every effort will be made to conduct a final study visit with the participant and participants will be followed clinically until, if applicable, all adverse events resolve.

- Withdrawal of consent.
- Withdrawal by the participant.
- Withdrawal by the investigator.
- Intercurrent illness or event that precludes further visits to the study site or ability to evaluate disease (e.g.-mental status change, large pleural effusion).
- Grade 4 or higher adverse events as defined by the CTCAE or life threatening AEs not covered by the CTCAE of the same preferred term related to the study medication, excluding conditions present at baseline or those directly related to skeletal complications of Osteogenesis Imperfecta.
- Clinically significant allergy or hypersensitivity to fresolimumab.
- Pregnancy.
- QTc interval of > 500msec.
- Clinically significant oral or mucosal bleeding with resulting hemoglobin of < 8g/dL.
- Development of keratoacanthoma, squamous cell or basal cell carcinoma.
- Development of any cancer.

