5.10 Quality Control: Study Related Procedures

Accurate, consistent and reliable data will be ensured through the use of standard practices and procedures. The DMCC will audit the Investigators' source data against eCRF entries and verify that the data are accurate.

6. Statistical Considerations

This study is designed to assess the safety and tolerability of fresolimumab in patients with Osteogenesis Imperfecta.

Sample Size: No formal sample size calculations were done for this study. The sample size was selected to allow for an initial assessment of safety in this population and dose range and feasibility of enrollment in this rare disorder. The sample size is 8 for the single dose study and 8 for the repeat dose study. The overall enrollment will be 16.

If needed, 2 additional patients will be enrolled in the repeat dose study to account for a drop-out rate of 20%.

Treatment-Related Adverse Events will be summarized by dose groups. Changes in vital signs, EKG, shifts in laboratory assessments and physical examinations, and patient-reported symptoms will be described. These will assess the primary endpoint of safety. Percent change in bone remodeling markers will be analyzed using a mixed model. BMD in the lumbar spine and the hip at 6 months for single dose study and 12 months for the multiple dose study will be compared to pretreatment levels using a Wilcoxon Signed Rank test. Percent change in the variables of the pulmonary function tests, and change in the 6-minute walk tests, and Numeric Rating Scale (NRS) for pain will be evaluated by Wilcoxon Signed Rank test. Values for derived pharmacokinetic variables, including Cmax, area under the curve, distribution, half-life (T1/2a), elimination half-life (T1/2b), clearance (CL), and volume of distribution at steady state (Vss), will be calculated as previously described and summarized by dose-group using descriptive statistics.

7. Data Management

The results from Screening and data collected during the study will be recorded in the

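### Section 5.7's Grade 4 stopping criterion can be read in more than one way, and one related death meets neither numeric criterion; clarify the wording and attach a dosing pause to it

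*Combined protocol and SAP*

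**What the plan says.** Section 5.7 opens its list with "This study may be suspended or closed if". Two entries are numeric. The first needs 2 or more subjects with Grade 4 or higher CTCAE events, or "life threatening AEs not covered by the CTCAE of the same preferred term related to the study medication", leaving out baseline conditions and direct skeletal complications of OI. The second reads "If 2 or more subjects develop cancer". The same section gives NIH, the DSMB and local IRBs standing power: they "have the authority to stop or suspend this trial at any time". It also lists the investigators' own safety judgment as a ground, with no count attached.

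Section 5.8, on discontinuing an individual subject, repeats the phrase: "Grade 4 or higher adverse events as defined by the CTCAE or life threatening AEs not covered by the CTCAE of the same preferred term".

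Section 4 (Design) says the DSMB's decision to go to 4 mg/kg rests on adverse events, safety data and the "discontinuation criteria outlined in sections 5.6 and 5.7 of the protocol". Section 5.6 deals with reporting unanticipated problems. The subject-level criteria are in 5.8.

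**The concern.** The first numeric criterion joins two kinds of event with an 'or' and puts two qualifiers at the end: same preferred term, and related to study drug. Nothing shows how far back either qualifier reaches. Two careful readers could look at the same safety data and disagree on whether the criterion is met, including when the DSMB decides on escalation.

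Section 5.8 does not settle the matter. It applies the phrase to one subject and gives no count of subjects or events, so there is nothing for the term to be the same as.

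The second gap is at the low end of the count. Whichever reading is taken, one death attributed to fresolimumab is one subject, and both numeric criteria need two.

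Stage 2 is where this matters most. Group 1 is infused at months 0, 3, 6 and 9, while scheduled DSMB review is every 6 months (Section 5.1). The Day 90, 180 and 270 procedures in Section 4.8 go on to infusion, and no text available for this review holds that infusion pending a safety review.

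**Working it through.** **Step 1: the readings, without any assumed rate.** Take (i) both qualifiers govern all events; (ii) same term governs only the non-CTCAE events, while relatedness governs all; (iii) both qualifiers govern only the non-CTCAE events. Apart from the listed exclusions, the criterion behaves as follows.

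| Situation | (i) | (ii) | (iii) |
|---|---|---|---|
| 2 subjects, related Grade 4, same term | met | met | met |
| 2 subjects, related Grade 4, different terms | not met | met | met |
| 2 subjects, unrelated Grade 4 (CTCAE) | not met | not met | met |
| 1 subject, related death | not met | not met | not met |

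Rows 2 and 3 change with the reading. Row 4 never meets the criterion, and it does not meet the cancer criterion either.

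**Step 2: how many subjects.** The plan has 8 + 8 = 16 (Section 6). Its dropout allowance reproduces: 8/(1 - 0.20) = 10, which is the stated "2 additional patients will be enrolled in the repeat dose study", so up to 16 + 2 = 18. The synopsis also says "Participants enrolled in Stage 1 of this study may be enrolled in Stage 2 of the study if they meet eligibility". If all 8 Stage 1 subjects re-enter, there could be as few as 8 distinct people.

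**Step 3: illustration.** Assumptions, none from the documents: independent subjects; a risk p per subject of a related Grade 4+ event; one such event per affected subject; k equally likely terms; a share f of these events fatal.

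- Any term: P(X ≥ 2), with X ~ Bin(n, p).
- Same term: 1 - Σ over m of C(n,m) p^m (1-p)^(n-m) × [k!/(k-m)!]/k^m, where terms with m > k are zero.
- Full proposed rule (two related Grade 4+ subjects, or one related death): P(X ≥ 2) + f × P(X = 1).

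For n = 16, k = 3, f = 5% to 20%:

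| p | Any term | Same term | P(X = 1) | Full rule |
|---|---|---|---|---|
| 1% | 1.1% | 0.4% | 13.8% | 1.8-3.8% |
| 2% | 4.0% | 1.5% | 23.6% | 5.2-8.7% |
| 5% | 18.9% | 8.4% | 37.1% | 20.8-26.3% |
| 10% | 48.5% | 27.1% | 32.9% | 50.2-55.1% |

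For example, at p = 5%: 0.1892 + 0.05 × 0.3706 = 0.2078, and 0.1892 + 0.20 × 0.3706 = 0.2634.

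**Step 4: sensitivity.** With k from 2 to 10 and n = 16, the same-term figure runs from 11.6% to 2.8% at p = 5%, and from 34.8% to 10.5% at p = 10%. With n = 18, any term against same term (k = 3) is 22.6% against 10.4% at 5%, and 55.0% against 32.3% at 10%. With n = 8 it is 5.7% against 2.2%, and 18.7% against 8.0%.

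**The case against.** The strongest reply is that the ambiguity changes nobody's powers. The list is permissive: meeting the criterion compels nothing and failing it blocks nothing. A reader might infer that one related death, or two related Grade 4 events under different terms, could not stop the trial. The documents do not support that. Standing authority and the investigators' safety ground both apply without a count. Fatal and life-threatening reportable SAEs go in within 24 hours (5.4). The Safety Officer reviews SAEs and can recommend action (5.5), and the team reviews adverse events monthly (5.1). The DSMB decides before 4 mg/kg and before Stage 2. At escalation it sees adverse events and safety data as well as the criteria, so a second event under another term would be in front of it either way.

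This stands, and it keeps the consequence small. It also means the percentages above show how often a non-binding criterion would be met, not how many subjects would be protected. At 1-2% risk the two readings differ by only 0.7 to 2.5 points (1.1 - 0.4 and 4.0 - 1.5).

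What the reply does not remove is the unclear wording, the stale cross-reference, and the fact that every listed safeguard needs someone to decide before the next infusion is held. Part of the drug-risk text in Section 5.3 was not available, so the absence of a hold is a statement about the text that could be read.

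**Conclusion.** The point holds in a limited form. From the text alone, the scope of the qualifiers in 5.7 is unclear, the phrase has no referent in 5.8, one related death meets neither numeric criterion, and Section 4 sends the DSMB to a section with no discontinuation criteria. None of this depends on an assumed rate. It is not a finding that the trial is unprotected.

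The size depends wholly on assumptions. With 16 subjects the choice of reading moves the chance of meeting the criterion by under 1 point at 1% risk and by about 21 points at 10% (48.5 - 27.1), with 3 equally likely terms. This should be corrected because two readers ought not to differ on a stopping criterion in a Phase 1 safety trial that redoses every 3 months. It is not a reason to hold the study.

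**What to change.** 1. **Reword the 5.7 criterion**, for example: *Two or more subjects each have an event attributed to study drug, whatever its preferred term, that is either CTCAE Grade 4 or above or, where the CTCAE does not list it, life-threatening. Baseline conditions and direct skeletal complications of OI do not count.* Same-term pairs are a subset of any-term pairs, so reading (i) loses nothing. Unrelated events, which reading (iii) would count, remain covered by the investigators' safety ground.
2. **Add a pause**: *Enrolment and dosing pause when this criterion is met, counting Stages 1 and 2 together, or when any subject has a fatal event attributed to study drug; no exclusions apply to deaths. Dosing resumes only after DSMB review and NIH agreement. An infusion delayed by a pause is given at the first visit after the pause is lifted and recorded as delayed.* NIH is named because the DSMB advises NIH on continuation (5.1).
3. **Reword 5.8** so that one Grade 4+ event, or one life-threatening event outside the CTCAE, attributed to study drug ends that subject's dosing. Keep the present exclusions.
4. **In Section 4**, cite 5.7 and 5.8 in place of 5.6 and 5.7.

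No new data are needed. The cost is occasional DSMB reviews, at the full-rule rates tabulated above for 16 subjects. With 18 subjects those become 24.5-30.2% at 5% risk and 56.5-61.0% at 10%. Related deaths in the excluded categories would add slightly to these figures. Some Stage 2 infusions could also slip past the ±14-day window and count as deviations under 7.5, in groups of only 4. A pause leads to review, not closure.
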